9.4. Type and Duration of Follow-up of Subjects after Adverse Events

AEs will be followed until resolution or stability even if this extends beyond the study-reporting period. Resolution of an AE is defined as the return to pretreatment status or stabilization of the condition with the expectation that it will remain chronic.

Follow-up procedures, evaluations, and outcomes will be recorded on the subject's case report forms.

Subjects who experience AEs consistent with COVID-19 through Day 540 for cohorts 1-4 and Day 365 for cohort 5 will be evaluated either by the site or by a health care provider to which the subject may be referred. Clinical specimens for SARS-CoV-2 RNA and serum for immunology (e.g., pro-inflammatory cytokine levels) assessments will be collected or requested to be collected using standardized methods. Assays of these specimens will be conducted at a central laboratory. Subjects will ideally be followed for as long as they continue to shed viral RNA. If feasible, other samples for concurrent or retrospective virologic assessments (e.g., the quantification of viral RNA in blood, rectal swabs, lower respiratory tract samples) will also be collected and analyzed.

9.5. Halting Rules

9.5.1. Halting Criteria for the Study

Study dosing can be halted at any time if medically indicated. Study dosing must be stopped, and a review of available safety data will be conducted by the SRC if any of the following occur:

- 1. Death of a dosed subject following injection and prior to the subject's last visit that was not the result of trauma or accident, and possibly related to study product.
- 2. Occurrence of a life-threatening allergic/hypersensitivity reaction (anaphylaxis) in any subject, manifested by bronchospasm with or without urticaria or angioedema or requiring hemodynamic support with pressor medications or mechanical ventilation.
- 3. One subject with an SAE that is considered possibly related or definitely related to study product.
- 4. Two or more subjects with a Grade 3 AE in the same organ class (systemic toxicity, clinical laboratory tests or vital signs) regardless of relatedness to study drug. An

exception to this includes scenarios where there are obvious and acceptable physiological explanations for a Grade 3 abnormality (e.g., Grade 3 hematuria in a menstruating female).

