Since this is a first-in-human study, administration of the study products to subjects in cohorts 1, 2 and 5 will occur to allow careful observation of individuals for adverse events. Two sentinel subjects within each cohort will be admitted and administered a dose on Day 1 to remain in the clinic until Day 2. The randomization scheme will be designed to ensure that one subject will receive ADM03820 and the other will receive placebo. The IM dosing of the remaining subjects within cohorts 1, 2, and 5 will not be initiated until at least 48 hours have passed and no adverse events have occurred that meet halting criteria, and no safety signals have occurred that in the opinion of the investigator warrant further investigation. The remaining subjects within each specific cohort will be dosed at least four hours apart until all subjects in the cohort have been dosed. An alternate subject will be admitted to the unit for each two-subject group. Dose escalation will not occur until safety data through Day 8 is reviewed by the SRC.

Cohort 1 (150 mg IM injection) will be dosed first. Two sentinel subjects (one ADM03820 and one placebo) will each be administered a single 3 mL IM injection. The dosing of the next subjects within Cohort 1 will not be initiated until at least 48 hours have passed and no adverse events have occurred that meet halting criteria and no safety signals have occurred that in the

opinion of the investigator warrant further investigation. The remaining subjects in the cohort will be dosed at least four hours apart until all subjects in the cohort have been dosed.

Dose escalation to Cohort 2 will not occur until safety data through day 8 for Cohort 1 is reviewed by the SRC. Objective dose escalation criteria and safety evaluations will be utilized.

In Cohort 2 (300 mg IM injection), two sentinel subjects (one ADM03820 and one placebo) will each be administered two 3 mL IM injections. Dosing for the remaining subjects in Cohort 2 will be initiated after at least 48 hours have passed and no adverse events have occurred that meet halting criteria and no safety signals have occurred that in the opinion of the investigator warrant further investigation. The remaining subjects in the cohort will be dosed at least four hours apart until all subjects in the cohort have been dosed.

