Dosing for Cohort 3 (300 mg IM injection) will not occur until safety data through day 8 for Cohort 2 is reviewed by the SRC. Objective safety evaluations will be utilized. Subjects in Cohort 3 will be scheduled based on the SRC recommendation and will each be administered two 3 mL IM injections without delay.

Dosing for Cohort 4 (300mg IM injection of drug product concentrated at 100mg/mL) will occur without delay. Subjects in Cohort 4 will be administered a single 3mL IM injection.

In Cohort 5 (600 mg IM injection of drug product concentrated at 100mg/mL), two sentinel subjects (one ADM03820 and one placebo) will each be administered two 3 mL IM injections. Dosing for the remaining subjects in Cohort 5 will be initiated after at least 48 hours have passed and no adverse events have occurred that meet halting criteria and no safety signals have occurred that in the opinion of the investigator warrant further investigation. The remaining subjects in the cohort will be dosed at least four hours apart until all subjects in the cohort have been dosed. The SRC will review safety data through day 8 for subjects in cohort 5 prior to the initiation of the phase 2 protocol.

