9.3.2. Serious Adverse Events

The following procedures will apply to all serious adverse events:

- The Principal Investigator will report any SAE to ICON PVSS within 24 hours of awareness.
- ICON PVSS will perform an initial check of the SAE and contact the site for any missing elements and then inform the ICON MM, and the ISM of the SAE.
- ICON PVSS will record the information on the appropriate serious adverse event report form and send to RGS
- Each SAE will be reviewed and followed to resolution or stability by a study physician
- SAEs will be collected on each subject up to 60 days after his/her last study visit.

Any AE that meets a protocol-defined serious criterion must be submitted immediately (within 24 hours of site awareness) on an SAE form to RGS at the following address:

ICON PVSS

ICON plc PVSS

[name] SAE Email Address: [name] [contact] SAE Fax Number (in case email is not available): [contact]

ICON PVSS will send AE/SAE information to Resilience Government Services, Inc.

Resilience Government ServicesResilience Government Services, Inc.13200 NW Nano CourtAlachua, FL 32615, USASAE [contact]SAE [contact]SAE Email Address: [contact]</t/>

Other supporting documentation of the event may be requested by RGS and should be provided as soon as possible.

ICON plc PVSS will send SAEs with the ICON Drug Safety Physician assessment of causality, expectedness, and any impact on the benefit-risk ratio of the IMP to RGS. The DOD will be notified of the SAE by RGS.

If the investigator becomes aware of an SAE that is suspected to be related to study product up to 60 days after the subject completes the study, the investigator will report the event to ICON PVSS.

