9.5.2. Dose Escalation Halting Criteria

If any of the following criteria are met, escalation to the next planned dose cohort will not proceed until all available study data have been reviewed by the SRC.

- More than 25% of the subjects in the cohort experience an AE, grade 2 or above in the same organ class
- A specific AE increases in severity from one cohort to the next AND the number of subjects reporting that AE (at the higher severity level) in the cohort is the same or greater. An exception would be headaches going from a grade 1 to a grade 2.

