9.5.3. Evaluation of Dose Escalation

The SRC must agree unanimously on the following criteria prior to dose escalation:

- A review of all available unmonitored and uncoded safety data from at least 7 subjects per cohort to Day 8, at a minimum, demonstrate that study halting criteria as outlined in Section 9.5.2 have not been met.
- A review of all available unmonitored and uncoded safety data from at least 7 subjects per cohort to Day 8, at a minimum, demonstrate that no safety signals of any nature were observed.

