9.6. Safety Oversight

9.6.1. Independent Safety Monitor (ISM)

The ISM is a physician with relevant expertise whose primary responsibility is to provide independent safety monitoring in a timely fashion. The ISM will review SAEs and other AEs as needed and provide an independent assessment.

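### Study-halt criterion 4 names Grade 3 with no floor: read literally, some same-class pairs that include a Grade 4 event force no dosing stop, although a pair of Grade 3 events does

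*Protocol*

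**What the plan says.** Protocol 9.5.1 requires a dosing stop and SRC review if any of four criteria is met:

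1. a non-accidental death that is possibly related;
2. anaphylaxis in any subject;
3. one SAE considered possibly or definitely related;
4. "Two or more subjects with a Grade 3 AE in the same organ class", irrespective of causality, except where a Grade 3 abnormality has an obvious and acceptable physiological cause.

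The section opens by allowing dosing to be halted on medical grounds at any point.

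Protocol 9.5.2 holds escalation if "More than 25% of the subjects in the cohort experience an AE, grade 2 or above in the same organ class", or if "A specific AE increases in severity from one cohort to the next" with at least as many subjects reporting it at the higher severity. Under 9.5.3 the SRC must agree unanimously that the data "demonstrate that no safety signals of any nature were observed". Under 9.6.4, if any halting criterion is met, the SRC meets and advises on whether further dosing is appropriate.

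On oversight, 9.3.2 has the safety group "inform the ICON MM, and the ISM of the SAE", and 9.6.1 states: "The ISM will review SAEs and other AEs as needed and provide an independent assessment".

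In Section 4, dosing after the two sentinels in Cohorts 1, 2 and 5 also requires that "no safety signals have occurred that in the opinion of the investigator warrant further investigation". Cohorts 3 and 4 have no sentinel step. For the latter: "Dosing for Cohort 4 (300mg IM injection of drug product concentrated at 100mg/mL) will occur without delay".

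The SAP (Section 3.0, study treatments and assessments) only refers back to protocol 9.5.

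**The concern.** This is a mandatory stopping rule in a first-in-human study, and on its literal wording it is not monotone in severity: a worse pair of events can escape a stop that a milder pair triggers. Apart from anaphylaxis, criterion 4 is the only one of the four that does not rest on a causality judgement, so that protection is lost at the higher grade. The point bears mainly on dosing within a cohort, after the sentinel step in Cohorts 1, 2 and 5 and throughout Cohorts 3 and 4. There, 9.5.1 is the only place where a stop is compulsory.

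**Working it through.** **The plan's own figures.** The protocol states no operating characteristic for the halting rule. The nearest figures, in 11.1, reproduce: 1 − 0.85^8 = 0.7275 (stated 0.728), 1 − 0.5^8 = 0.9961 (stated 0.996), and 1 − 0.025^(1/8) = 0.3694 (stated 0.369). They describe detecting any toxicity among eight active subjects and do not depend on criterion 4.

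**Is a floor supplied elsewhere?**
- 9.5.2, the next section, writes one at Grade 2, so adjacent rules are worded differently. Its headache exception treats a move from Grade 1 to Grade 2 as a rise in severity, so a higher number means a worse event.
- 9.2.1 adopts CTCAE v5.0, but Appendix B gives only a link.
- 11.3.3.1 counts a subject at the worst severity, which does not treat a Grade 4 event as a Grade 3 one. That rule governs summaries, not halting.
- The SAP adds nothing.

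No current text says that Grade 3 includes Grade 4 for halting.

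**Applying the four criteria.** Take two subjects with events in the same organ class, no anaphylaxis and no death, both events having the same seriousness and causality. As written, criterion 4 needs grade = 3 in at least two subjects.

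| Pair | Non-serious, not related | Non-serious, related | Serious, not related | Serious, related |
|---|---|---|---|---|
| 3+3 | stop (criterion 4) | stop (4) | stop (4) | stop (3 and 4) |
| 3+4 | none | none | none | stop (3) |
| 4+4 | none | none | none | stop (3) |

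The 3+3 pair forces a stop in 4 of 4 columns; the 3+4 and 4+4 pairs do so in 1 of 4. With grade ≥ 3, all three pairs force a stop in 4 of 4. If the two events differ in status, a single related SAE is enough for criterion 3, so a pair escapes only when neither event is a related SAE.

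**Which cells are firm?** The serious, not-related column rests on the protocol text alone. The non-serious columns do not. Section 9 has seriousness and severity assessed separately, but 9.1 counts life-threatening and important medical events as serious, and the grade definitions are not reproduced. The documents therefore do not show which Grade 4 events could be non-serious.

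**Does 9.5.2 catch the pair?** In a full cohort, 2/10 = 20%, which is not more than 25%. A third subject with a Grade 2 or worse event in that class gives 3/10 = 30% and meets the first bullet. The ratio 2/7 = 28.6% would also exceed 25%, but seven is the minimum number reviewed under 9.5.3, whereas the bullet counts subjects in the cohort. The second bullet is met if the same AE goes from Grade 3 in one cohort to Grade 4 in the next with equal counts. It is not met by two Grade 4 events within one cohort, nor by different AEs in one class. When either bullet is met, escalation is held and the SRC advises on further dosing, but no stop within the cohort is compelled.

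**The case against.** The strongest reply is that this is a wording slip with little practical reach.

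- Dosing may be halted on medical grounds at any time (9.5.1). The Medical Monitor and the Medical Lead may each ask for the SRC to be convened over any safety concern (9.6.2, 9.6.3).
- A 4+4 pair of SAEs escapes only if both are judged not related. Section 9.2.2 says the product must always be under suspicion and reserves that category for events with no reasonable possibility of causation. A drug safety physician also assesses causality (9.3.2), and criterion 3 does not say whose judgement counts.
- The Independent Safety Monitor reviews SAEs. Section 9.5.2 does more than hold escalation, because 9.6.4 has the SRC advise on further dosing. Although 9.6.4 lets escalation go ahead when no halting criterion is observed, 9.5.3 still requires unanimous agreement that there is no safety signal.

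All of this stands and makes the gap narrow. What it does not do is oblige anyone to stop dosing within a cohort, which is the function of 9.5.1.

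A reader might infer more than the documents support:
- *That dosing would in practice continue after two Grade 4 events.* The discretionary routes above make that unlikely, and nothing suggests it was intended.
- *That non-serious Grade 4 laboratory values fall in the gap.* This cannot be confirmed without the grading table.
- *That 44 of 50 subjects (3 × 8 + 2 × 10) are unprotected.* That counts planned positions outside the six sentinel places, not subjects whom a halt could still protect.

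**Conclusion.** The point holds as a defect in the wording of a mandatory safety rule. On a literal reading, a same-class 3+4 or 4+4 pair triggers no compulsory stop if it includes no anaphylaxis, no possibly or definitely related SAE and no possibly related death; a 3+3 pair does trigger one. The firmest instance is Grade 4 SAEs judged not related.

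The conclusion assumes that the criterion is applied as written and that the grades are ordered by severity. A floor was very probably intended, and many readers would apply one, but a compulsory first-in-human rule should not depend on that inference.

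No magnitude is claimed. The frequency of such events cannot be obtained from the documents. Each subject receives a single dose, so a halt helps only those not yet dosed, and the number remaining under version 7.0 is not stated. If none remain, the change would have no effect on dosing in this study.

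**What to change.** In protocol 9.5.1, criterion 4, insert *or above* after Grade 3 and leave the rest of the criterion unchanged, including its application irrespective of causality. Keep the physiological-explanation exception limited to Grade 3, so that it does not widen to higher grades.

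The cost is a short protocol amendment with IRB approval (14.2) and possibly an extra dosing pause for SRC review. The SAP needs no edit because it refers back to protocol 9.5. Sample size and analyses are unaffected.

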9.5.2. Dose Escalation Halting Criteria

If any of the following criteria are met, escalation to the next planned dose cohort will not proceed until all available study data have been reviewed by the SRC.

- More than 25% of the subjects in the cohort experience an AE, grade 2 or above in the same organ class
- A specific AE increases in severity from one cohort to the next AND the number of subjects reporting that AE (at the higher severity level) in the cohort is the same or greater. An exception would be headaches going from a grade 1 to a grade 2.

9.5.3. Evaluation of Dose Escalation

The SRC must agree unanimously on the following criteria prior to dose escalation:

- A review of all available unmonitored and uncoded safety data from at least 7 subjects per cohort to Day 8, at a minimum, demonstrate that study halting criteria as outlined in Section 9.5.2 have not been met.
- A review of all available unmonitored and uncoded safety data from at least 7 subjects per cohort to Day 8, at a minimum, demonstrate that no safety signals of any nature were observed.

9.6. Safety Oversight

9.6.1. Independent Safety Monitor (ISM)

The ISM is a physician with relevant expertise whose primary responsibility is to provide independent safety monitoring in a timely fashion. The ISM will review SAEs and other AEs as needed and provide an independent assessment.

9.6.2. ICON Medical Monitor

The ICON Medical Monitor (MM) is the clinical site's primary point of contact for eligibility or safety related questions. The ICON MM is responsible for liaising with RGS ML to ensure that all medical concerns are communicated and will provide any potential pertinent medical communication update to the project team as needed. The ICON MM will participate in the planned SRC meetings and can make a recommendation that the SRC be convened to review any safety concerns.

9.6.3. Resilience Government Services Medical Lead

The RGS ML will be the main point of contact for the ICON MM and the DOD for any safetyrelated questions or concerns. The RGS ML will escalate any medical or safety concerns to the DOD as needed. The RGS ML will participate in the planned SRC meetings and can make a recommendation that the SRC be convened to review any safety concerns.

9.6.4. Safety Review Committee (SRC)

The SRC will be composed of:

- PI, or designee
- RGS ML
- ICON Medical Monitor or designee;

Objective dose-escalation criteria and safety evaluations will be utilized. Prior to dose escalation, the SRC will evaluate unmonitored and uncoded safety and tolerability data for at least 7 subjects out to Day 8 to determine whether dose escalation can occur. If none of the events described in 9.5.1 Study Halting Criteria or in 9.5.2 Dose Escalation Halting Criteria are observed, dose escalation will proceed. Should any of the study halting criteria or dose escalation halting criteria be met, the SRC will meet to evaluate the data and recommend appropriateness of further dosing. The SRC recommendation to advance to the next level will be documented and provided to all the appropriate parties (PI, RGS, and ICON) involved with the study.

If 4 or more subjects withdraw prior to Day 8, those subjects need to be replaced to ensure that data for at least 7 subjects are available for review.

If 4 or more subjects withdraw prior to Day 60 or are not compliant with all PK draws through Day 15, they may be replaced.

If more than 2 subjects withdraw following the Day 8 SRC review of safety data, the site will attempt to replace those subjects in that dose group at the time of the next planned cohort.

10. CLINICAL MONITORING

10.1. Site Monitoring Plan

Site monitoring is conducted to ensure that the human subject protection, study and laboratory procedures, study intervention administration, and data collection processes are of high quality and meet sponsor, GCP/ICH and, when appropriate, regulatory guidelines. Site visits may be conducted by an authorized representative of ICON, the IRB, HRPO, other regulatory or government agencies to inspect study data, subjects' medical records, and eCRFs in accordance with ICH guidelines, GCP and the respective local and national government regulations and guidelines.

The investigator will permit authorized representatives of ICON and the respective local and national health authorities to inspect facilities and records relevant to this study, if needed.

A separate monitoring plan, to be developed by ICON, will describe protocol-specific items to be monitored.

11. STATISTICAL CONSIDERATIONS

11.1. Sample Size Considerations

This is a Phase 1 study first in humans with five dosing cohorts and no formal sample size calculations based on testing a statistical hypothesis were constructed. Sample sizes are consistent with this type of early phase study. Dosing groups of ten participants each, eight participants assigned the active group and two assigned to the control group for each cohort are practical and provide sufficient information for a total sample size of 50 for a Phase 1 trial primarily designed to assess safety.

The dosing groups of eight participants in the active group has a probability of at least one subject experiencing an event of toxicity ranges from 0.728 to 0.996 assuming true event rates are between 0.15 and 0.5.

Additionally, if no events are observed in each scenario described above, the upper bound of an exact 95% confidence interval for the true proportion is 0.369.

11.2. Planned Interim Analyses

There are several blinded interim analyses planned for this study. A blinded interim analysis is planned to analyze all PK samples through Day 30 for all subjects in Cohorts 1 and 2. A second blinded interim analysis is planned to analyze all PK samples after all subjects in cohorts 1-3 complete Day 60. A third interim analysis is planned to analyze safety and PK data after all subjects in cohort 5 complete Day 60.

There is also an interim clinical study report (CSR) planned after subjects in Cohorts 1 through 4 complete Day 90.

Stopping criteria are for safety and are defined in section 9.5. No adjustments for multiplicity will be made at these interim analyses.

11.3. Final Analysis Plan

A formal statistical analysis plan will be developed with mock tables, listings, and figures. The ICH Guidance Document E9 (Statistical Principles for Clinical Trials) will be followed for all statistical content. For categorical data, summaries of frequencies and percentages will be presented. Summaries for continuous data will include minimum, lower quartile, median, mean, standard deviation, upper quartile, and maximum.

